6.7 Follow-Up Procedures

6.7.1 Blood Draws

Subsequent to randomization, patients will be followed clinically and radiographically. A detailed medical and physical examination with blood draws for PSA, LDH, CBC w/Diff, Serum Chemistry panel (CMP), ctDNA (CAPP-seq), immune cell profiling (ImmunoSEQ), CTCs (EPIC HD-CTC), immunophenotyping, and testosterone will be performed within the first month, months 3, 6 and 12 (from date of randomization) for all patients. Correlatives at outside sites are optional and not mandatory. In-clinic visits are not required otherwise, unless indicated by laboratory tests. For men randomized to the SABR + Radium-223, they will also receive monthly CBCs as per standard of care for radium-223 infusions (within 7-10 days of radium-223 injection). Following 12-months patients will be followed by any physician as per standard of care which may include but not be limited to every 3-6 month clinic visits, laboratory evaluations for PSA and imaging, if appropriate. Further labs and imaging is at the discretion of the treating physician. This information of two year followup will be collected by the clinical study team for all participating sites.

Correlative science blood draws will be performed as above (details for these blood draws are contained within the APPENDIX III-V).

Briefly:

CAPP-Seq: 30-ml whole blood in purple top (EDTA) tubes (see APPENDIX III for details). The blood is stored in a freezer, then shipped in batches as per APPENDIX III. Baseline, months 3, 6 and 12 from randomization for both arms.

EPIC HD-CTC: 4-10 ml Streck Cell-Free DNA BCT tubes (see APPENDIX IV for details). Whole blood is shipped out the same day as it is drawn as per APPENDIX IV. Baseline and day 180 from all men.

ImmunoSEQ: 10-ml whole blood in purple top (EDTA) tubes (see APPENDIX V for details). The patient samples are stored in a 80 Degree Celsius freezer and shipped in batches as per APPENDIX V. Baseline and day 90 from all men.

Immunophenotyping: 2-10-mL whole blood in green top (heparin) tubes (see APPENDIX VIII for details).

Only participating sites that have the resources to do so, will participate in blood draw collection and shipment.

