6.7.2 Imaging

Bone scan and CT/MRI of metastatic site(s) will be at 6- and 12-months for all patients, unless indicated more frequently by clinical or laboratory findings.

If applicable, bone scan and ¹⁸F-DCFPyL (“PyL”) -PET/CT of metastatic site(s) will be at 6 months for all patients, unless indicated more frequently by clinical or laboratory findings. The results of the ¹⁸F-DCFPyL (“PyL”) -PET/CT will be made available to the treating physicians prior to enrollment to determine treatment.

The CT portion of the ¹⁸F-DCFPyL (“PyL”) -PET/CT scans at 6 months will be used to determine radiographic response based on RECIST 1.1 criteria for soft tissue lesions. Similarly, the CT or MRI scans at 6- and 12-months will be used to determine radiographic response based on RECIST 1.1 criteria for soft tissue lesions.

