Q.	After randomization, only interval concomitant medications, interval medical history, and limited physical exam information needs to be collected. This only needs to occur once, either on Day 1 visit or during SABR treatment.
R.	Per SOC, patient's will have a PSMA PET/CT prior to enrollment/randomization. Patients who are still enrolled in the trial will have a PSMA PET/CT 360 Days from initial PSMA PET/CT (see S).
S.	ONLY for sites participating in PSMA PET-CT: If applicable, patient's will have a PSMA PET/CT 12 Months from the second completed PSMA PET (~approximately 13/14 months from randomization)
T.	Additional follow-up visits are for 1 year. Follow up after 12 months will be conducted Q6 months, as SOC (months 18 and 24).
U.	All AEs will be collected using CTCAE version 4.0. All skeletal related events will need to be collected throughout the trial and during the follow-up period.
V.	If Pre-study and Day 1 occurs within 2 weeks of each other, the following labs do not need to be repeated for Day 1: PSA, LDH, Testosterone, CBC w/Diff, and CMP. If PSA is completed within 2 weeks from Day 1, regardless of Footnote D, then it may be used. If PSA has been drawn greater than 2 weeks from Day 1, then it must be repeated. Research Blood for Day 1 MUST be completed PRIOR to SABR and/or Xofigo (Radium-223) injection.
W.	During 18 and 24 month follow-up: limited physical exam, ECOG (performance status) changes to conmedications, changes to medical history, Adverse Events, BPI (QoL), and PSA are required for documentation (Epic Note). Any additional labs or imaging are at the discretion of the treating physician.

STUDY CALENDAR: SBRT + Xofigo ARM

	Pre-Study ^Y	Day 1 ^Y	Day 15	Day 29	Day 43	Day 57	Day 61	Day 71	Day 85	Day 31 (+/- 7 days)	Day 39	Day 113	Day 127	Day 141	Day 155	Day 181 (+/- 7 days)	Day 361 (+/- 7 days)	Follow-up Q6 Month ^W (+/- 7 days)
ICF	X																	
Demographics	X																	
Medical History	X									X ^T						X ^T	X ^T	X ^Z
Concomitant Medications	X									X ^T						X ^T	X ^T	X ^Z
Physical Exam	X									X ^T						X ^T	X ^T	X ^Z
Performance Status	X									X ^F						X	X	X ^Z
Vital Signs	X									X								
Height	X									X								
Weight	X									X								
CBC w/ Diff ^A	X ^C									X ^I						X	X	X ^Z
LDH	X ^C									X ^I						X	X	X ^Z
Serum Chemistry ^B	X ^C									X ^I						X	X	X ^Z
Testosterone	X ^C									X ^I						X	X	X ^Z
PSA	X ^D									X ^I						X	X	X ^Z
Bone Scan	X ^E									X ^I						X	X	X ^Z

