W.	Additional follow-up visits are for 1 year. Follow up after 12 months will be conducted @6 months, as SOC (months 18 and 24)
X.	All AEs will be collected using CTCAE version 4.0. All skeletal related events will need to be collected throughout the trial and during the follow-up period.
Y.	If Pre-study and Day 1 occurs within 2 weeks of each other, the following labs do not need to be repeated For Day 1: PSA, LDH, Testosterone, CBC w/Diff, and CMP. If PSA is completed within 2 weeks from Day 1, regardless of Footnote D, then it may be used. If PSA has been drawn greater than 2 weeks from Day 1, then it must be repeated. Research Blood for Day 1 MUST be completed PRIOR to SABR and/or Xofigo (Radium-223) injection.
Z.	During 18 and 24 month follow-up: limited physical exam, ECOG (performance status) changes to conmedications, changes to medical history, Adverse Events, BPI (QoL), and PSA are required for documentation (Epic Note). Any additional labs or imaging are at the discretion of the treating physician.

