9. MEASUREMENT OF EFFECT

9.1 Antitumor Effect – Metastatic Tumors

For the purposes of this study, patients should be re-evaluated for radiographic response 6- and 12-months after randomization. Trial radiologists evaluating for treatment responses will be blinded to the treatment group and treatment specifics (lesions treated with SABR).

Response and progression will be evaluated in three ways:

- 1) Using Response Evaluation Criteria in Solid Tumors (RECIST 1.1) Committee definition. Changes in only the largest diameter (uni-dimensional measurement) of the tumor lesions are used in the RECIST criteria.
- 2) Lesions by bone scan will be evaluated as positive, negative or no change. MRI of the bone lesion can be used to clarify equivocal lesions.
- 3) Serial PSA changes.

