9.5.5 Clinical Response Parameters

Progression is a composite endpoint defined from the Prostate Cancer Working Group 2 (PCWG2) criteria for metastatic castrate resistant prostate cancer (mCRPC) (75) and our previous trials in a population of men with biochemical failure without metastases (72-74). Progression will be defined as either: 1) a $\geq 25\%$ increase in PSA from nadir (and by ≥ 2 ng/mL), requiring confirmation ≥ 4 weeks later (PCWG2 criteria); and/or, 2) clinical/radiographic-progression defined as symptomatic progression (worsening disease-related symptoms or new cancer-related complications), or radiologic progression (on CT scan: $\geq 20\%$ enlargement in sum diameter of soft-tissue target lesions [RECIST 1.1 criteria]; on bone scan: ≥ 1 new bone lesions), initiation of ADT or death due to any cause, whichever occurs first. Death is considered a severe adverse event here.

Progression Free Survival (PFS) is defined as the time from starting treatment to the time of progression as defined above. Subjects who do not progress will be censored at the time of the last contact.

ADT Free Survival (ADT-FS) is defined as the time from starting treatment to the time of initiation of palliative ADT. ADT will typically be initiated on tumor progression and/or development of new metastases. Subjects who do not start ADT will be censored at the time of the last contact.

Time to Progression (TTP) is defined as the time from starting treatment to the time of first documented tumor progression or new lesions by CT and/or bone scan or initiation of ADT. Subjects who do not progress will be censored at the time of the last contact. In addition, death from any cause will also be censored.

Time to New Metastasis (TNM) is defined as the time from starting treatment to the time of a new documented tumor metastasis by CT and/or bone scan. Subjects who do not progress will be censored at the time of the last contact.

Overall Survival (OS) is defined as the time from starting treatment until death due to any cause. For subjects who do not die, time to death will be censored at the time of last contact.

Locoregional Control (LRC) is defined as the time from starting treatment until local and/or regional relapse is documented

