14.2 Sample Size/Accrual Rate/Follow-Up

The primary endpoint will be progression-free survival (PFS). Data from STOMP and ORIOLE on this patient population indicate that $\geq 50\text{-}60\%$ would show progression as defined above within a 12-month period from SABR, and a median PFS around 10 months. (72-74). We hypothesize that the addition of radium-223 will be able to reduce the risk of progression by 50%. A sample size using a 1:1 randomization scheme of 30 patients per arm will provide 80% power to detect an increase of median PFS from 10 months to 20 month (corresponding to hazard ratio 0.5) with type I error = 0.1, using one-sided log-rank test. The calculation assumes 18 months of accrual time with an additional follow-up of 12 months after the last patient is randomized. To account for 5% early drop out, we will randomize a total of 64 patients (32 per arm).

There will be no interim analysis for futility, since the progression endpoint will not have been reached by a meaningful number of patients before full accrual.

Follow-up (Every 3-6 months for 24 months or until death)

Patients will be followed for 2 years after Day One of trial or until death. Patients withdrawn from the study because of AEs will be followed until the adverse event has either resolved or stabilized. Reasons for premature withdrawal should be determined and noted.

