14.5 Analysis of Secondary Objectives

- For safety analysis, adverse events will be summarized by type and grade.
- Kaplan-Meier (KM) estimates will be used to summarize ADT-free survival (ADT-FS), time to locoregional progression (TTLP), time to distant progression (TTDP), time to new metastasis (TNM) and duration of response over time. The median PFS, ADT-FS, TTLP, TTDP TNM and duration of response will be reported.
- The efficacy of SABR + Radium-223 in men with oligometastatic disease will also be determined by measuring local control of each lesion at 12-months.

Each metastatic lesion will be considered a target lesion and independently evaluated for response using RECIST 1.1 or bone scan evaluation criteria above. The lesion will be coded as being locally controlled if it is considered stable radiographic disease or if there is evidence of a partial or complete response. Local control assessment will start at three months following randomization and continuous assessment will be pursued during the follow-up period. The proportion of the lesions that have a stable or better response will be estimated using generalized estimating equation.

- Quality of life will be assessed using the Brief Pain Inventory form. An overall score will be calculated pre-treatment and at the time of the 2nd radiologic reassessment. The change in score will be evaluated with a paired t-test.

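### Time to new metastasis needs a scan but is censored at last contact, so unscanned time in months 12 to 24 counts as metastasis-free; the bias depends on who is scanned late

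*Combined protocol and SAP*

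**What the plan says.** - **Event and censoring.** Section 9.5.5 runs TNM from the start of treatment to a "new documented tumor metastasis by CT and/or bone scan. Subjects who do not progress will be censored at the time of the last contact".
- **Required imaging.** Section 6.7.2: "Bone scan and CT/MRI of metastatic site(s) will be at 6- and 12-months for all patients", or more often if clinical or laboratory findings call for it. Section 9.1 agrees: "patients should be re-evaluated for radiographic response 6- and 12-months after randomization".
- **Follow-up.** Section 14.2: "Patients will be followed for 2 years after Day One of trial or until death". The section 8 calendar notes put the later visits at months 18 and 24: "Follow up after 12 months will be conducted Q6 months, as SOC (months 18 and 24". Those visits require a limited examination, ECOG status, medication and history changes, adverse events, the pain inventory and PSA.
- **Imaging after month 12.** Section 6.7.1: "Further labs and imaging is at the discretion of the treating physician". The notes to both calendars say the same: "Any additional labs or imaging are at the discretion of the treating physician".
- **Analysis.** Section 14.5 plans Kaplan-Meier summaries: "The median PFS, ADT-FS, TTLP, TTDP TNM and duration of response will be reported". It gives no other censoring rule for TNM. Section 14.4 censors PFS at the last scan, but that sentence covers PFS only.

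**The concern.** None of the items required at months 18 and 24 can register a TNM event. A man last scanned at month 12 and seen at month 24 still stays in the risk set for 12 months in which an event could be recorded only if someone chose to scan him. Metastases in unscanned men go uncounted, and those men remain in the denominator for events found in men who were scanned.

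Sections 3.3 and 14.1.2 frame the objective as SABR versus SABR + Radium-223, and the trial is not blinded. Section 9.1 blinds the radiologists who read the scans, but they do not decide who is scanned. If late scanning differs between arms for reasons unrelated to disease, the curves can separate without any difference in spread.

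**Working it through.** **The plan's own figure.** No rate, event count or sample size is stated for TNM. The PFS calculation in 14.2 reproduces: medians of 10 and 20 months, 18 months' accrual plus 12 months' follow-up and 30 men per arm give event probabilities 0.751 and 0.509. That is 30 × 0.751 + 30 × 0.509 = 37.8 events. Schoenfeld's formula needs 38, and power is 80.2% at one-sided 0.10. The sample size is not in question.

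**Assumptions for TNM** (not in the documents): exponential time to new metastasis with a 20-month median; every man scanned at months 6 and 12 and contacted to month 24; a metastasis is found at the first scan after it arises.

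**True curve.** S(t) = exp(−t·ln 2/20), so S(12) = 0.660, S(18) = 0.536 and S(24) = 0.435. New metastases arise in a = 0.660 − 0.536 = 0.124 of men in months 12 to 18 and in b = 0.536 − 0.435 = 0.101 in months 18 to 24.

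**Last-contact censoring.** Nobody is censored before month 24, so the estimate is one minus the proportion detected. Let p be the chance that a man who has a new metastasis is scanned at each late visit:

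estimate at 24 = S(12) − [1 − (1 − p)²]·a − p·b

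- p = 0: 0.660. No events are recorded after month 12; the curve is a flat tail.
- p = 0.3: 0.660 − 0.51 × 0.124 − 0.3 × 0.101 = 0.566.
- p = 0.6: 0.660 − 0.84 × 0.124 − 0.6 × 0.101 = 0.495.
- p = 0.9: 0.660 − 0.99 × 0.124 − 0.9 × 0.101 = 0.447.

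Only p enters this formula. The scan chance r of men without a new metastasis does not matter under last-contact censoring.

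**Last-scan censoring.** Here r does matter, because men free of disease leave the risk set when they are not scanned. For p = 0.9 and r = 0.3:

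- Month 18: events 0.9 × 0.124 = 0.112. Men still at risk (scanned at 18 or 24): 0.99 × 0.124 + (1 − 0.7 × 0.1) × 0.101 + 0.51 × 0.435 = 0.438.
- Month 24: events 0.1 × 0.9 × 0.124 + 0.9 × 0.101 = 0.102. At risk: 0.102 + 0.3 × 0.435 = 0.232.
- Estimate: 0.660 × (1 − 0.112/0.438) × (1 − 0.102/0.232) ≈ 0.277.

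| Late scanning (p / r) | True | Last contact | Last scan |
|---|---|---|---|
| none | 43.5% | 66.0% (flat tail) | curve ends at month 12 |
| 0.3 / 0.3 | 43.5% | 56.6% | 41.0% |
| 0.6 / 0.6 | 43.5% | 49.5% | 42.5% |
| 0.9 / 0.3 | 43.5% | 44.7% | 27.7% |
| 0.8 / 0.2 | 43.5% | 46.0% | 22.2% |
| 0.7 / 0.3 | 43.5% | 47.7% | 30.0% |

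The same formulas with other medians:

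- **15 months (true 33.0%):** last contact gives 47.2% and 39.4% at p = r = 0.3 and 0.6. In the three disease-triggered rows it gives 34 to 37%, and last scan 15 to 21%.
- **30 months (true 57.4%):** the corresponding figures are 68.2% and 62.4%, 58 to 61%, and 35 to 44%.

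**Arm comparison with no treatment effect.**

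- Scanning unrelated to disease, 0.6 in SABR and 0.3 in SABR + Radium-223: last contact reports 49.5% against 56.6%, a gap of about 7 points. In a large-sample simulation with a 10-month median in both arms, scanning 75% of control and 25% of experimental men turned a true hazard ratio of 1.0 into 0.82 under last contact; reversing the fractions gave 1.21. Last scan stayed at 1.00.
- Men with metastases scanned at 0.9 in both arms, others at 0.6 against 0.3: last contact gives 44.7% in both arms. Last scan gives 38% against 28%.

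**Month 12.** The estimate is S(12) = 66.0% under either rule and any late-scanning pattern, because both arms have a required scan there.

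**The case against.** The strongest reply is that the plan points to scans prompted by findings. Section 6.7.2 allows extra imaging on clinical or laboratory grounds, 6.7.1 foresees imaging where appropriate, and PSA is required at months 18 and 24. If late scans mostly follow disease, last contact is close to the truth and last-scan censoring is well below it. This stands. It rules out simply extending the PFS rule of 14.4 to TNM. It does not rescue the stated rule, which is accurate only if the scanning is triggered and sensitive, and nothing in the plan secures that.

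Four stronger readings are tempting, and the documents do not support them:

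- *Nobody looks for metastases after month 12.* Discretionary imaging is foreseen, two-year follow-up information is collected (6.7.1), and participating sites have a PSMA PET/CT at about 13 to 14 months, although the TNM definition names only CT and/or bone scan. If truly no one were scanned, both rules would give the same Kaplan-Meier steps and the same log-rank result; only the flat tail and the numbers at risk would mislead.
- *The promised medians mainly reflect scanning frequency.* A median of 12 months or less is fixed by the required scans. Only a later one is exposed: at an assumed 20 months, last contact gives not reached when 25% or 50% of men are scanned at both late visits, where last scan gives 24 months.
- *The false-positive rate is inflated.* Section 14.5 plans no between-arm test of TNM, so no error rate attaches to it.
- *Time to distant and locoregional progression carry the same error.* No censoring rule is stated for them. That is a gap to fill.

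**Conclusion.** The point holds for a secondary endpoint. The stated rule credits men with metastasis-free time during which no scan was required, and 14.5 offers no alternative. Under an assumed 20-month median, the month-24 estimate is too high by about 6 to 13 points when 60 to 30% of men are scanned at each late visit regardless of disease, by about 22 points as a flat tail with no late scans, and by only about 1 to 4 points when scanning is mostly disease-triggered. Unequal scanning unrelated to disease also distorts the arm comparison. With equal late scanning, or none, the comparison is essentially unaffected.

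These sizes rest on an exponential model, assumed medians and assumed scan chances, none of which the documents supply. The existence of the fault does not depend on them; its size and the better censoring rule do. A reader might infer that censoring at last scan is the correct rule. The calculations do not support that for months 12 to 24, since under triggered scanning it understates the rate by about 14 to 21 points. Only the estimate through month 12 is sound under both mechanisms. Primary PFS and the sample size are unaffected.

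**What to change.** In 9.5.5 and 14.5:

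1. Make the reported TNM estimate the proportion free of new metastasis through the month-12 scan. Censor men without that scan at their last adequate CT or bone scan, and report how many there are per arm and why, since 6.11 and 6.15 allow removal at progression.
2. Show months 12 to 24 as descriptive only, with the number of men scanned per arm.
3. Give last-contact and last-scan censoring as sensitivity analyses, stating that last-scan censoring is informative if scans are triggered.
4. State the same approach for time to distant and time to locoregional progression.
5. State whether a new lesion seen only on PSMA PET/CT counts as a TNM event.

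The cost is wording, with no new visits or scans. The downside is that a TNM median beyond 12 months would be reported as not estimable. The change should be made before the data are analysed, because a censoring rule chosen afterwards would be open to challenge.

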9.5.6 Response Review

All responses will be reviewed by the study co-investigator radiologists.

10. ADVERSE EVENT REPORTING REQUIREMENTS

10.1 General

Adverse event collection and reporting is a routine part of every clinical trial. This study will use the descriptions and grading scales found in the NCI Common Terminology Criteria for Adverse Events version 4.0 (CTCAE v 4.0) that is available at <http://ctep.cancer.gov/reporting/ctc.html>.

Information on all adverse events, whether reported by the participant, directly observed, or detected by physical examination, laboratory test or other means, will be collected, recorded, followed and reported as described in the following sections.

Participants should be instructed to report any serious post-study event(s) that might reasonably be related to participation in this study. The investigator should notify the IRB and any other applicable regulatory agency of any unanticipated death or adverse event occurring after a participant has discontinued or terminated study participation that may reasonably be related to the study.

10.2 Definitions

10.2.1 Adverse Event (AE)

An adverse event is any undesirable sign, symptom or medical condition or experience that develops or worsens in severity after starting the first dose of study treatment or any procedure specified in the protocol, even if the event is not considered to be related to the study.

Abnormal laboratory values or diagnostic test results constitute adverse events only if they induce clinical signs or symptoms or require treatment or further diagnostic tests.

10.2.2 Serious adverse event (SAE)

A serious adverse event is an undesirable sign, symptom, or medical condition which:

- is fatal or life-threatening;
- requires or prolongs inpatient hospitalization;
- results in persistent or significant disability/incapacity;
- constitutes a congenital anomaly or birth defect; or
- jeopardizes the participant and requires medical or surgical intervention to prevent one of the outcomes listed above.

Events **not** considered to be serious adverse events are hospitalizations for:

- routine treatment or monitoring of the studied indication, not associated with any deterioration in condition, or for elective procedures
- elective or pre-planned treatment for a pre-existing condition that did not worsen
- emergency outpatient treatment for an event not fulfilling the serious criteria outlined above and not resulting in inpatient admission
- respite care

